4.3.3 Imputation Rules for Laboratory Values Outside of Quantification Range

Values of the form “< x” (i.e., below the lower limit of quantification [LLOQ]) or “> x” (i.e., above the upper limit of quantification [ULOQ]) will be imputed as “x” in the calculation of summary statistics but displayed as “< x” or “> x” in the listings.

4.4 Software Programs

All report outputs will be produced using SAS® version 9.4 in a secure and validated environment. PK analyses will be produced using Phoenix® WinNonLin (WNL) version 8.1 or later in a secure and validated environment.

All report outputs will be provided to the Sponsor. Tables and figures will be combined in one PDF document and listings in another.

4.5 Study Patients

4.5.1 Disposition of Patients

A listing will be created for subjects discontinued from the study using the ENR. An additional listing will be created for subjects completing the study using the RND. Both listings will include the standardised disposition term and the date of disposition event.

A summary table will be created and will include, in addition to the number of patients enrolled, the number and percentage of patients who:

- were randomised
- were not randomised
- received at least a dose of the first treatment
- completed the first treatment
- discontinued the first treatment
- received at least a dose of the second treatment
- completed the second treatment
- discontinued the second treatment
- completed study
- were withdrawn from the study for any reason (one row in the table for all reasons)
- were withdrawn from the study for each reason (one row in the table for each reason).

4.5.2 Protocol Deviations

Important protocol deviations (IPD) may lead to the exclusion of participants from the PP and the PKAS. Deviations will be defined before database lock. Important deviations will include the following:

- Violation of inclusion and/or exclusion criteria
- Administration of prohibited concomitant medications expected to influence the primary endpoint
- Receiving incorrect study intervention than randomised to.

All protocol deviations will be discussed at a data review meeting prior to database lock in order to define the analysis sets for the study. All IPDs will be listed by participant.

The Protocol Deviation Specifications will be followed to assess which protocol deviations are important in a Data Review Meeting (DRM) shortly before database lock/unblinding. A DRM report detailing the assessment of protocol deviations, AEs, the assignment of participants to analysis sets and the exclusion of data from specific analyses will be signed by all scientific experts.

The number and percentage of patients in the FAS meeting each IPD criterion will be summarised by cohort. Patients deviating from an IPD more than once will be counted once for that criterion. Any patients who have more than one IPD will be counted once in the overall summary.

The number of enrolled patients included/excluded from each of the analysis sets will be summarised. Patients and data excluded from each analysis set will be listed with the reason (such as the specific IPDs or AEs) for exclusion.

4.6 Analysis Sets

The following sets are defined:

Population/Analysis set	Description
All enrolled subjects (ENR)	All participants who signed informed consent prior to any study-related procedures.
All randomised subjects (RND)	All participants in the ENR randomised to one of the two sequence groups within a cohort. The ENR will be analysed according to the planned sequence or treatment.
Full Analysis Set (FAS)	All participants in the RND who received at least one dose of study intervention. The FAS will be analysed according to the planned treatment and will be used as the primary population for reporting pharmacodynamic data and to summarize baseline characteristics. Any important deviations from randomised treatment will be listed and considered when interpreting the pharmacodynamic data.
Safety Analysis Set (SAF)	All participants in the RND who received at least one dose of study intervention. The SAF will be analysed according to the actual treatment.
Per Protocol Analysis Set (PP)	All participants in the FAS who did not have an important protocol deviation considered to have an impact on the analysis of the primary endpoint and who completed the study. The PP will be analysed according to the actual treatment received.
PK Analysis Set (PKAS)	All participants in the FAS with at least one quantifiable AZD9567 concentration and no important protocol deviations, or AEs considered to have an effect upon PK. Participants may be excluded from the PK population if they have an AE of vomiting before 2x the median t _{max} of the group. The PKAS will be analysed according to the actual treatment.

4.7 Demographics and Baseline Characteristics

Demographic characteristics (age, sex, race, ethnicity, country) and baseline patient characteristics (height, weight and BMI) will be listed and will be summarised by cohort in the SAF and FAS. In

addition to presenting descriptive statistics for age, the summary table will present the number and percentage of patients per age group (18-44, 45-64 and 65-75 years).

4.8 Baseline, change from baseline and percentage change from baseline definitions

Demography and baseline characteristics

For demography and baseline characteristics other than weight, the baseline will be the assessment at screening. For weight, the baseline will be the assessment at Day -1 performed by means of the **CCI** device. If the weight at Day -1 is missing, the weight at Day -2 (or at Screening, in the case of period 1 if the value at Day -2 is also missing) will be the baseline for such a period.

Pharmacodynamics

Change in AUC(0-4)

In the case of the linear mixed models for the change from baseline in glucose AUC(0-4) (primary endpoint), hormones related to glucose homeostasis (insulin, glucagon, GLP-1, GIP), FFAs and C-peptide (secondary endpoints), the baseline measurement will be the AUC(0-4) on Day -1 (i.e., prior to first dosing) of each period.

Glucose concentrations assessed by CGM

For the calculation of the rise in mean glucose and the mean daily glucose, the baseline will be the average of the values from -24 hours to first dosing on Day 1 (values from -72 to -24 hours will be excluded from the baseline) of each period.

For the MMRM for the rise in mean glucose and the mean glucose, the baseline included as a covariate in the model will be the value -24 hours to first dosing on Day 1 of each period.

MMTT derived first phase insulin response

For the calculation of the change from baseline of insulin, glucose and C-peptide included in the calculation of $\Delta I10/\Delta G10$, $\Delta I30/\Delta G30$, $\Delta C10/\Delta G10$ and $\Delta C30/\Delta G30$, the baseline will be value at Day -1 of each period.

24-hour U-Na and U-K

For Na and K and the Na/K ratio, the baseline will be the value at Day -1 in each period.

CCI [Redacted]

[Redacted]

[Redacted]

[Redacted]

[Redacted]

[Redacted]

[Redacted]

[Redacted]

[Redacted]

Safety

ECG and vital signs

For ECG and vital signs, the baseline will be the pre-dose assessment at Day 1 in each period. If this value is missing the value closest in time prior to Day 1 within the same visit (or at Screening, in the case of period 1) will be the baseline for such a period.

Clinical chemistry/haematology/urinalysis

For the safety laboratory assessments, the baseline for the calculation of the change from baseline will be the pre-dose assessment at Day 1 in each period. If this value is missing, the value closest in time prior to Day 1 within the same visit (or at Screening, in the case of period 1) will be the baseline for such a period.

For the linear mixed models for Na, K and Na/K, the baseline included as covariate will be the same as that used to calculate the change from baseline.

CCI [Redacted]

[Redacted]

[Redacted]

CCI [Redacted]

CCI

Serum cortisol and ACTH

For the calculation of the difference in the concentration of each of these hormones between Days -1 and 4 of each period, the baseline will be value on Day -1. If the concentration of ACTH at Day -1 in period 1 is missing, the concentration at the Screening visit will be the baseline for such a period.

4.9 Medical History

The Full Analysis Set will be used for the presentation of the data.

Medical history data will be listed by patient.

A summary of the number and percentage of patients with any relevant medical history will be presented by SOC and PT, by treatment sequence.

Relevant surgical history will be listed in the same manner.

Medical history data of diabetes will be listed by patient including start date and end date or on going.

4.10 Prior and Concomitant Medications, and other treatments

All listings and tables will be based on the Safety Analysis Set.

Medications will be coded using the World Health Organisation-Drug Dictionary (WHODRUG) and will be classified by Anatomical Therapeutic Chemical (ATC) categories.

Exclusively prior medications are those that started and stopped prior to the first dose of the investigational medicinal product (IMP) in the first treatment period and those that started and stopped after 21 days after the last dose in the first period and before the first dose of IMP in the second period. Medications taken between the first dose and up to 21 days after the last dose in any period are concomitant (including medications that started prior to dosing and continued after).

Concomitant medication will be listed by participant and will include the reported name, anatomical therapeutic chemical (ATC), route of administration, total dose, frequency, start date/time, duration, whether or not ongoing and indication and will be summarised by ATC and PT.

CCI**CONFIDENTIAL****Project Document Version No.** Final 2.0**Project Document Effective Date:** <Date of last signature>

Page 29 of 56

Medications ongoing during both the periods will be counted under both Period 1 and Period 2.

Prior and concomitant use of Metformin will be listed by participant and will include the total dose, frequency, start date/time, duration and whether or not ongoing and will be summarised by ATC and PT.

The number of subjects taking concomitant medications under each treatment will be summarised by ATC classification/ Generic term.

The duration will be calculated as:

Duration (in days) = (end date – start date) + 1, if only date is known.

4.11 Safety and Tolerability Evaluation

The actual treatment will be used for all safety and tolerability analyses. All listings and tables will be based on the Safety Analysis Set.

The listings of the safety data (AEs, laboratory data, vital signs, and ECG) will include scheduled and unscheduled assessments.

4.11.1 Adverse Events

Within each cohort, AEs will be assigned as having taken place after each of the two treatments if the start of the AE is after the first dose of the treatment but before the end of 21 days after the last dose (i.e., the end of Day 24, in the case of subjects whose last dose was on Day 3). AEs on Day 1 with a missing start time will be assumed to have started after the first dose.

In order to assign the corresponding SOC and preferred term to each AE, AEs will be coded using the Medical Dictionary for Regulatory Activities (MedDRA) Version 22.1 or higher.

AEs occurring prior to the time of dosing on Day 1 and after 21 days after the last dose will not be included in summaries.

An AE listing for the Safety analysis set will cover details for each individual AE. A summary table with the number of AEs, by SOC and PT will be created.

The following summaries for the number and percentage of participants will be created:

- Number of subjects with adverse events in any of these categories:
 - Any AE
 - Any AE with outcome = death
 - Any SAE (including events with outcome = death)
 - Any AE leading to discontinuation of IP
 - Any AE leading to drug interruption
 - Any AE leading to withdrawal from study
- Number of subjects with adverse events, by SOC and PT
- Number of subjects with adverse events, by PT
- Number of subjects with adverse events leading to discontinuation of investigational product, by system organ class and preferred term.

In summaries including SOC or PT, the summaries will first be sorted by decreasing percentage of participants in each SOC and PT within SOC, and then alphabetically by SOC, and PT within SOC.

The following summaries for the number and percentage of adverse will be created:

- Number of adverse events by system organ class and preferred term.

4.11.2 Deaths and Serious Adverse Events

The number of SAEs, by SOC and PT will be summarised.

These summaries will be created for the number of subjects and adverse events, by SOC and PT.

4.11.3 Clinical Laboratory Evaluation

All values will be classified as low (below range), normal (within range), or high (above range) based on central laboratory reference ranges.

The Na/K ratio will be calculated at each timepoint and this ratio will be included in clinical chemistry listings and tables. All clinical laboratory results will be listed.

The comparison of the effect of treatment on changes in Na, K and Na/K will be analysed by means of the same statistical model as that used for the analysis of the primary endpoint.

For haematology, clinical chemistry and coagulation a table with descriptive statistics of absolute values and changes from baseline for each laboratory variable over time. Only planned tests will be summarized. In the case of the urinalysis, individual measurements will be listed and a summary table

of the baseline versus maximum value on-treatment (ie, a shift table) will be created.

The on-treatment definition will be based on the on-treatment definition used for AE.

4.11.4 Vital Signs, ECGs

Vital Signs

Vital signs data will be listed by participant including changes from baseline. Flags for a clinically significant assessment will be provided in the listing.

Descriptive statistics for absolute values and changes from baseline will be presented by treatment and by cohort.

ECGs

All ECG parameters will be listed by participant including changes from baseline for numeric ECG parameters. Abnormalities in ECG will also be listed.

Descriptive statistics for absolute values and changes from baseline will be presented by treatment and cohort. The on-treatment definition will be based on the on-treatment definition used for AE.

The number and percentage of participants under each treatment exceeding the following ICH boundaries of QTcF will be tabulated:

- Absolute value > 450 msec and > 480 msec
- Increase from baseline > 30 msec and > 60 msec.

This summary table will also include the number and percentage of participants under each treatment exceeding the following values:

- Absolute value >450 msec and Increase from baseline >30 msec
- Absolute value >500 msec and Increase from baseline >60 msec.

The following figure will be provided for each ECG parameter:

- Box-plot by treatment and day

4.11.5 Morning serum cortisol and ACTH

The morning serum cortisol and ACTH will be listed and tables with descriptive statistics for the value -15 minutes prior to the mixed meal on Days -1 and 4 (in each period) and change from baseline will be created.

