Clinical chemistry (including triglycerides and HDL-C)	X		X		X			X			X	X				X	X	Section 8.3.4 Fasting sample not required for Day -2 and Day 26
Coagulation (INR, PT and aPTT)	X																	Section 8.3.4
Serology (HIV I and II, HAV, HbsAg and HCV antibody, tuberculosis)	X																	Section 8.3.4
HbA1c	X																	Section 8.3.4
Pregnancy test (hCG)	X																X	Section 8.3.4. Females only

Visit	1	2	Visit 3 a						Washout (3 weeks) b	4	Visit 5 a						6	Comments
Phase	Screening	Outpatient visit	Residency in Unit a							Outpatient visit	Residency in Unit 2 a						Final/ET visit c	
Timing	≤ 14 days before start of IMP d	DAY														Follow-up 30 +/- 4 days after last dose of IMP		
		-4	-2	-1	1	2	3	4		24 (-4)	26 (-2)	27 (-1)	28 (1)	29 (2)	30 (3)	31 (4)		
TNFα j							X								X		
 
• Pre-dose
 
• Post-dose 1, 2, 4, 8, 12, 24 hoursk
 
• Section 8.2.4
 
	
PK (AZD9567)							X	X							X	X	
 
• Pre-dose
 
• Post-dose 0.25, 0.5, 1, 1.5, 2, 3, 4, 6, 8, 12, 24, 30 hoursk
 
• Section 8.6.1
 
	
PK (prednisolone)							X	X							X	X	
 
• Pre-dose
 
• Post-dose 0.25, 0.5, 1, 1.5, 2, 3, 4, 6, 8, 12, 24, 30 hoursk
 
• Section 8.6.1
 
	
Genetic research			X														Section 8.8 and Appendix D	

Visit	1	2	Visit 3 a						Washout (3 weeks) b	4	Visit 5 a						6	Comments
Phase	Screening	Outpatient visit	Residency in Unit a							Outpatient visit	Residency in Unit 2 a						Final/ET visit c	
Timing	≤ 14 days before start of IMP d	DAY														Follow-up 30 +/- 4 days after last dose of IMP		
		-4	-2	-1	1	2	3	4		24 (-4)	26 (-2)	27 (-1)	28 (1)	29 (2)	30 (3)	31 (4)		
MMTT				X				X				X				X	A standardised mixed meal will be administered around 0700 after an overnight fast. Blood samples to be taken 15 mins pre- and 10, 20, 30, 60, 75, 120, 180, 240 min post-mixed meal intake (see Section 5.3.1) for analysis of plasma glucose, insulin, C-peptide, GLP-1, GIP, glucagon and FFAs, see Sections 1.3.1, and 8.2.2	
Serum cortisol				X			X	X			X			X	X	X	Sample to be taken at 0800 	
CCI				X			X	X			X			X	X	X	Sample to be taken at 0800 	

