**Table 1 Risk Assessment**

Potential Risk of Clinical Significance	Summary of Data/Rationale for Risk	Mitigation Strategy
Study Intervention		
Glucose homeostasis	Glucocorticoid class effects: It is well known that GCs stimulate gluconeogenesis and inhibit the glucose uptake in muscle and adipose tissue. Increased glucose levels and tissue insulin resistance is observed early after exposure with GCs.	Glucose insulin and C-peptide will be measured to evaluate the effects on glucose homeostasis.
Hypothalamus, pituitary gland, and adrenal glands (HPA)-axis	Reduction in plasma cortisol is a physiological and expected response to administration of an exogenous GR agonist. Clinically relevant adrenal insufficiency after a 3-day course of GR agonist treatment is not expected.	Serum cortisol and ACTH will be measured to evaluate effects of AZD9567 on cortisol levels.
Effect on mineralocorticoid axis	Prednisolone has a known effect on the mineralocorticoid axis so it may be	Morning plasma CCI to evaluate salt

Potential Risk of Clinical Significance	Summary of Data/Rationale for Risk	Mitigation Strategy
	expected that AZD9567 could have an impact	and water retention, will be measured.
Drug-drug interactions	AZD9567 showed a moderate inhibitory potential on drug transporters in in vitro assays and there is a low to moderate risk for drug-drug interactions.	Drugs with transporter mediated absorption such as digoxin should be excluded. Where statins are used, AZD9567 is taken in the morning and the statin in the evening.
Gastrointestinal (GI) effects	Bleeding of the stomach or intestines is an infrequent side effect of long-term treatment of prednisolone. Animal studies have shown that GCs impair both gastric mucus production and gastric bicarbonate secretion which results in weakening of gastric mucosal defences.	Participants with history of previous gastric/duodenal ulcers or surgery affecting the upper GI tract are excluded. Monitoring for GI bleeding will be performed by symptomology, and laboratory testing (haemoglobin measurement).
Fluid and electrolyte disturbances; sodium retention	Long-term administration of GCs can cause fluid and electrolyte disturbances and sodium retention.	Electrolyte balance will be monitored through routine safety laboratory tests.

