To explore the relationship between AZD9567 exposure and inhibition of LPS-stimulated TNF $\alpha$ release for high and low dose comparison (Cohort 1 and Cohort 2)	
 
TNF<math>\alpha</math> concentrations
 

Safety	
To evaluate the safety and tolerability of AZD9567 compared to prednisolone	
 
AEs/SAEs
 
Vital signs
 
ECGs
 
Changes in clinical chemistry/haematology parameters
 
Morning serum cortisol
 
ACTH
 

Exploratory	
CCI [REDACTED]	[REDACTED]
CCI [REDACTED]	[REDACTED]
CCI [REDACTED]	[REDACTED]

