#### **9.4.3 Safety**

Safety will be assessed by descriptive analysis of AEs/SAEs, vital signs, ECGs and clinical laboratory assessments.

Serum cortisol and ACTH will be analysed in a similar manner to the TNF $\alpha$  secondary endpoint. Further details on statistical analyses will be provided in the SAP.

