4.15 Changes in the Conduct of the Study or Planned Analysis

The following changes to the statistical methodology planned in Study Protocol will be applied:

- The repeated measures mixed model will also include the time term.

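### Cortisol and ACTH: the protocol contradicts itself on whether treatments are compared, and the SAP settles it without saying so, leaving no treatment contrast and no summary of Day 3 or Visit 6

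*SAP*

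**What the plan says.** **Purpose.** Protocol Table 1 lists the HPA axis as a potential risk and gives as its mitigation: "Serum cortisol and ACTH will be measured to evaluate effects of AZD9567 on cortisol levels". The same row adds: "Clinically relevant adrenal insufficiency after a 3-day course of GR agonist treatment is not expected". In protocol Table 2, morning serum cortisol and ACTH are endpoints of the objective "To evaluate the safety and tolerability of AZD9567 compared to prednisolone".

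**Protocol analysis text.** Section 9.4.3 first describes the other safety data as descriptive. It then says "Serum cortisol and ACTH will be analysed in a similar manner to the" TNF-alpha secondary endpoint and leaves details to the SAP. Section 9.4.2.2 sets out the TNF-alpha method: an AUC, tables of the AUC and of each sampling point, and an ANOVA comparing treatments within cohort. The synopsis (Statistical methods), however, includes both hormones in its list of safety variables assessed descriptively.

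**Sampling.** The Schedule of Activities places cortisol and ACTH on Days -1, 3 and 4 of each period and at the final visit, with ACTH also at screening. The stated time is "Sample to be taken at 0800". On meal-test days a footnote moves the draw to the fasting sample 15 minutes before the meal.

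**SAP.** Section 4.8 defines the baseline as Day -1, "For the calculation of the difference in the concentration of each of these hormones between Days -1 and 4 of each period", with Screening ACTH as the fallback in period 1. Section 4.11.5 provides listings and "tables with descriptive statistics for the value -15 minutes prior to the mixed meal on Days -1 and 4 (in each period", plus change from baseline. The over-time laboratory tables in 4.11.3 name haematology, clinical chemistry and coagulation, whereas the laboratory variable table in 3.2.2 puts both hormones under a different class. Section 4.15 declares one change from the protocol: "The repeated measures mixed model will also include the time term".

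**The concern.** The objective is comparative and the design is a crossover, so each completer supplies a direct within-person comparison of AZD9567 and prednisolone on adrenal suppression. The SAP reports each treatment separately and never estimates the difference. A study report written to this plan could describe cortisol and ACTH under each treatment, but it would have no planned estimate or interval with which to say how far they differ.

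The change is also not visible. Someone reading protocol 9.4.3 expects an ANOVA. Someone reading SAP 4.15 is told that only the time term in the repeated-measures model has changed. In addition, the one late sample after the second treatment goes to listings without a summary.

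**Working it through.** The plan gives no figure to reproduce on this point. The check sets the texts side by side, then counts samples and sizes the missing interval.

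**1. Analysis promised and analysis planned**

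| Source | Tables | Treatment comparison |
|---|---|---|
| Protocol synopsis | Descriptive | None stated |
| Protocol 9.4.3 read with 9.4.2.2 | Each measurement point | ANOVA |
| SAP 4.11.5 | Day -1, Day 4, change | None |
| SAP 4.15 | No entry | No entry |

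The TNF-alpha AUC cannot carry over, because TNF-alpha is sampled serially on one day and the hormones are single morning samples. The per-timepoint tables and the treatment comparison can. TNF-alpha is measured in Cohorts 1 and 2 only, so 9.4.3 implies between 2 hormones x 2 cohorts = 4 and 2 x 3 = 6 contrasts. The SAP plans 0.

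**2. Samples scheduled and tabulated, per completer**

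- Cortisol scheduled: Days -1, 3, 4 in 2 periods, plus Visit 6 = 3 x 2 + 1 = 7.
- Cortisol tabulated: Days -1 and 4 in 2 periods = 4.
- Listed only: 7 - 4 = 3 (Day 3 twice, Visit 6 once), and 3/7 = 43%.
- Over the 40 planned completers: 3 x 40 = 120 values, of which 80 are Day 3 and 40 are Visit 6.
- ACTH: 8 scheduled (the same 7 plus screening), 4 tabulated. Screening ACTH serves only as a fallback baseline.

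**3. What the untabulated samples show**

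- Day 3 is a dosing day. Dosing is at about 07:00 (± 30 min) and the sample at 08:00, so it falls about 1 hour after the dose (30 to 90 minutes). It is an on-treatment value.
- Visit 6 is 30 ± 4 days after the last dose, that is, 26 to 34 days. It is the only sample later than the morning after the last period 2 dose.
- Period 2 Day -1 is study Day 27. The last period 1 dose is on Day 3, so this tabulated sample comes 27 - 3 = 24 days after it, at the same pre-meal time as the period 1 baseline. It already gives recovery information after the first treatment.

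**4. Clock time**

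Day -1 and Day 4 draws are at about 07:00 - 15 min = 06:45. Day 3, Visit 6 and Screening ACTH are at 08:00. The tabulated Day -1 to Day 4 change therefore compares like with like. A change from Day -1 to Day 3 or to Visit 6 would not. The only place where the plan itself mixes the two times is the Screening fallback for a missing period 1 ACTH baseline.

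**5. Precision of the omitted contrast**

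For a balanced two-period crossover, the 95% CI half-width is t(0.975, n-2)/sqrt(n), in units of the SD of the within-participant difference:

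- Cohort 1, n = 24: 2.074/4.899 = 0.42 SD.
- Cohorts 2 and 3, n = 8 each: 2.447/2.828 = 0.87 SD.

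The documents give no SD for cortisol or ACTH, so these cannot be turned into concentration units.

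**The case against.** The strongest reply is that the SAP does follow the protocol, in its synopsis version. Section 9.4.3 also opens by describing safety as descriptive and defers detail to the SAP. This stands to the extent that the inconsistency starts in the protocol. A reader might infer that the SAP alone discarded a settled comparison, and the documents do not support that. It does not remove the problem, because 9.4.3 treats the two hormones in a separate sentence and the SAP chose between conflicting texts without recording the choice.

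Other replies limit the point:

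- **The data are not lost.** SAP 4.11.5 lists the hormones, and 4.11.3 lists all clinical laboratory results and classifies values against reference ranges. A reader might call 43% of the cortisol samples wasted, but what is missing is a summary.
- **Recovery is not ignored.** Period 2 Day -1 is tabulated, and Day 3 was never a recovery sample. Only Visit 6 is left out in that respect.
- **The expected clinical risk is small.** The risk table calls a fall in cortisol an expected response and does not anticipate clinically relevant insufficiency after 3 days.
- **Restricting the tables to pre-meal samples keeps clock time constant.** This is a good reason not to compute change to Day 3 or Visit 6. It is no reason to leave those values unsummarised.
- **Small cohorts say little.** At n = 8 the interval is wide, and protocol 9.1 already treats significance testing in Cohorts 2 and 3 as exploratory.

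One might also try to put a figure on the precision lost by reading the two treatment summaries as unpaired. That would rest on an assumed within-participant correlation and on a test the SAP does not plan, so it is not a measured defect.

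**Conclusion.** The point holds as an undeclared inconsistency with a real analytical consequence. Protocol 9.4.3 implies a treatment comparison of cortisol and ACTH, the synopsis does not, and SAP 4.11.5 adopts the second without an entry in 4.15. The result is 0 between-treatment estimates for a named endpoint of a comparative safety objective, and 3 of 7 cortisol samples per completer outside any visible summary table, including the only late sample after period 2.

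It does not show that adrenal safety goes unmonitored, that data are discarded, or that recovery is unexamined after both treatments. The primary analysis is unaffected.

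Two limits apply. Parts of SAP 4.8 and 4.12.2 are redacted, so absence from other tables is judged on visible text; 4.11.5 itself is intact. The precision figures assume equal sequence groups and complete data.

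**What to change.** Reconcile the protocol synopsis, protocol 9.4.3 and SAP 4.11.5 so that all three describe the same analysis. Then:

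1. **Contrast.** In SAP 4.11.5 add, per cohort and for each hormone, a within-participant comparison of the change from Day -1 to Day 4, with treatment, period, sequence and participant in the model and a 95% CI. A log scale is an option. Label it exploratory, and state that Cohorts 2 and 3 are imprecise. The SAP already fits its primary-endpoint model to Na, K and Na/K in 4.11.3, so this is within its own practice.
2. **Tables.** Summarise Day 3 by treatment, marked as 08:00 and about 1 hour after dosing, and Visit 6 by sequence. Do not compute change from the 06:45 Day -1 baseline for either.
3. **Baseline flag.** Mark any period 1 ACTH baseline taken from the 08:00 Screening sample.
4. **Record.** Enter the choice in SAP 4.15. If the database is already locked, SAP Section 1 provides for an addendum and discussion in the study report.

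The cost is SAP wording and a few extra tables from samples already scheduled, with no new procedures. The downside is more exploratory comparisons without multiplicity adjustment, which is why they need that label.
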